11.1. NYHA

The trend of NYHA classes during time will be assessed by means of:

- shift tables from preoperative to annual post-operative FU assessments (from 1 year FU to 5 year FU) by treatment group;
- a generalized linear model for longitudinal data on ordinal scale in order to model the probabilities of having lower NYHA response levels during time. The model will include the treatment covariate and the visit assessment as covariates, and the response categories for the NYHA will be considered in following order: Class I, Class II, Class III, and Class IV. An unstructured correlation structure will be defined in order to allow the model to take into account the dependency of repeated observations within each subject. The odds ratio of Perceval being in lower NYHA categories compared Standard valve will be shown.

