8.5.2 INCLUSION CRITERIA

Subjects who meet all the following criteria will be included:

1. The subject has an indication for treatment by valve replacement with a bioprosthesis according to the IFU, through either full sternotomy or mini-sternotomy.
2. The subject has aortic valve disease that can be treated with a commercially available Perceval valve size, based on preoperative CT-scan.
3. The subject has:
 - a) critical aortic valve area defined as an initial aortic valve area of $\leq 1.0 \text{ cm}^2$ or aortic valve area index $< 0.6 \text{ cm}^2/\text{m}^2$

AND

 - b) Mean gradient $> 40 \text{ mmHg}$ or $V_{\text{max}} > 4 \text{ m/sec}$ by resting echocardiogram or simultaneous pressure recordings at cardiac catheterization [or with dobutamine stress, if subject has a left ventricular ejection fraction (LVEF) $< 55\%$] or velocity ratio < 0.25 ;
4. The subject is symptomatic due to aortic stenosis with functional class of NYHA II or higher.
5. The subject has signed the informed consent.
6. The subject is of legal minimum age.
7. The subject will be available for postoperative follow-up beyond one year.

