8.6. OTHER BASELINE CHARACTERISTICS

For parameters collected on more than 1 occasion during the study including baseline, the assessment at baseline will be presented with assessments collected later on in the study and not in a separate table. These parameters are:

- NYHA class
- Signs of Infections
- Modified Rankin Scale
- NIHSS Score
- Vital signs
- Electrocardiogram (ECG)
- Site Reported Echocardiographic Values:
 - Aortic Mean Pressure Gradient (MPG), Aortic Peak Pressure Gradient (PPG), Sub aortic gradient, Left Ventricular Ejection Fraction (LVEF), Effective Orifice Area (EOA), Effective orifice area indexed (EOAi), Aortic Peak Velocity (VmaxAORTIC), LVOT Velocity max (VmaxLVOT), Doppler velocity index, LV mass, and Septum thickness.
 - Paravalvular and Central Leaks
 - MPG classification (section 18.12)
- Core-lab Reported Echocardiographic Values:
 - Aortic Mean Pressure Gradient (MPG), Aortic Peak Pressure Gradient (PPG), Mean Pressure Gradient, LVOT Peak Pressure Gradient, Mean Gradient (P2-P1), Peak Gradient 4(V2A- V2L) Left Ventricular Ejection Fraction (LVEF), Effective Orifice Area (EOA), Effective orifice area index (EOAi), Left Ventricular Mass, Left Ventricular Mass Index, Left Ventricular End Diastolic Volume, Left Ventricular End Systolic Volume, Aortic Peak Velocity (VmaxAORTIC), LVOT Velocity max (VmaxLVOT), Cardiac Output, and Cardiac Index.
 - Paravalvular and Central Leaks
- Health status (EQ-5D-5L)

For each time point, a radar chart will be created representing on the radii the mean level of each dimension.
- Blood test
 - Blood test results
 - Clinical significance of blood test values

NYHA, Echocardiographic values, Health Status, and Blood test will be analyzed to assess the trend during time. Additional details in section 11.1, 11.2, 0, and 13.2 respectively.

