Descriptive statistics of the change from baseline of the QALY and EQ-5D index values (continuous) at each FU assessment will be shown as described in section 5.2.

Linear mixed model for repeated measures (MMRM) will be applied to compare EQ-5D index values between the two groups. EQ-5D index values will be adjusted by baseline index value, time point, and treatment-by-time interaction. Patient will be also added to the model as a random variable. Estimates of the least square means for EQ-5D index values and 95 % confidence intervals (CIs) will be calculated by each visit and group.

Descriptive statistics of the change from baseline of the EQ VAS data (continuous) at each FU assessment will be shown as described in section 5.2.

Mann-Whitney tests will be applied to compare treatments in terms of EQ-5D index values and EQ VAS data.

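### SAP 11.1 does not say whether preoperative NYHA is a modelled visit: if it is, the odds ratio is diluted, and if it is not, baseline class goes unused

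*SAP*

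**What the plan says.** SAP 11.1 plans two analyses of NYHA class over time. The first is descriptive: "shift tables from preoperative to annual post-operative FU assessments (from 1 year FU to 5 year FU) by treatment group". The second is a generalized linear model for longitudinal ordinal data, in which "The model will include the treatment covariate and the visit assessment as covariates". Dependence within a patient is handled as follows: "An unstructured correlation structure will be defined in order to allow the model to take into account the dependency of repeated observations within each subject". One effect measure is reported: "The odds ratio of Perceval being in lower NYHA categories compared Standard valve will be shown". No baseline NYHA term and no treatment-by-visit term is listed, and the model text does not name the visits that supply responses.

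SAP 8.6 is the only other guide. It lists NYHA among the parameters for which "the assessment at baseline will be presented with assessments collected later on in the study and not in a separate table", and it points to section 11.1 with the sentence "NYHA, Echocardiographic values, Health Status, and Blood test will be analyzed to assess the trend during time".

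Elsewhere the same SAP uses baseline as a covariate. For EQ-5D (section 12.3), "EQ-5D index values will be adjusted by baseline index value, time point, and treatment-by-time interaction". The hemodynamic model in 11.2.1 also includes the baseline measurement. Protocol 8.5.2 sets the entry range for NYHA: "The subject is symptomatic due to aortic stenosis with functional class of NYHA II or higher".

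**The concern.** Preoperative NYHA class is collected by design, and the SAP leaves open how the model uses it.

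If it enters as a response, the treatment main effect has to cover a visit before implantation, where randomization makes the expected difference zero. A model with no treatment-by-visit term then averages that zero into the reported odds ratio. That visit should also contain no class I patients, because entry requires class II or higher. A common visit shift across all class boundaries would therefore fit it poorly.

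If it does not enter at all, a measurement likely to be prognostic is left out of the comparison.

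Two statisticians following 11.1 faithfully could therefore report different odds ratios from the same data. In either case, a single odds ratio cannot show whether a difference in functional class is early or sustained.

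**Working it through.** The documents give no NYHA distribution, effect size or power, so there is no figure of the plan's own to reproduce. The sizes below rest on stated assumptions.

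**Inputs from the documents.** NYHA is scheduled preoperatively, at 1–3 months, at 1 year and then yearly to 5 years (Protocol 4.2). That is 1 pre + 2 post visits to 1 year and 1 pre + 6 post to 5 years. Allocation is 1:1, the maximum N is 1234 and attrition is 10% (Protocol 8.5.7, 10.2, 10.3), so 1234 × 0.9 / 2 ≈ 555 per arm.

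**Assumptions, not in the documents.**
- Preoperative classes II/III/IV: 45/47/8%.
- Control post-operative classes I/II/III/IV: 60/33/6/1%.
- Latent correlation 0.5 between post-operative visits.
- Latent correlation between baseline and post-operative visits: 0.3 for dilution, varied from 0.2 to 0.6 for adjustment.

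**Reading A: the preoperative visit is a response.** Cumulative-logit data were simulated with 150,000 patients per arm and fitted with visits treated as independent.

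| True post-operative OR | Reported, 1 pre + 2 post | Reported, 1 pre + 6 post |
|---|---|---|
| 1.3 | 1.18 | 1.24 |
| 1.5 | 1.28 | 1.40 |
| 2.0 | 1.54 | 1.77 |
| Shrinkage of log OR | 35–37% | 16–17% |

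A hand check agrees. Under proportional odds, a visit's information is roughly proportional to 1 − Σp³, where p are the class proportions.
- Preoperative: 1 − (0.45³ + 0.47³ + 0.08³) = 0.805.
- Post-operative: 1 − (0.60³ + 0.33³ + 0.06³ + 0.01³) = 0.748.
- Weight on the preoperative visit: 0.805 / (0.805 + 2 × 0.748) = 0.35 with two post-operative visits, and 0.805 / (0.805 + 6 × 0.748) = 0.15 with six.

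The SAP specifies an unstructured correlation, which changes the weights. With m post-operative visits, pre–post correlation 0.3, post–post correlation 0.5 and equal variances, generalized least squares gives weights x (pre) and y (each post) that solve x + 0.3my = 1 and 0.3x + [1 + 0.5(m − 1)]y = 1. The shrinkage is x / (x + my).
- m = 2: y = 0.530 and x = 0.682, so 0.682 / 1.742 = 39%.
- m = 6: y = 0.236 and x = 0.574, so 0.574 / 1.993 = 29%.

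The ranges are therefore about 35–39% (1 pre + 2 post) and 16–29% (1 pre + 6 post).

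**Reading B: post-operative visits only.** One post-operative visit was simulated with 555 per arm, true OR 1.5 (log OR 0.405), classes III and IV merged, and 3,500 replicates. Relative efficiency is the squared ratio of mean estimate to its standard deviation, adjusted against unadjusted.

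| Baseline correlation | Unadjusted log OR (SD) | Adjusted log OR (SD) | Relative efficiency |
|---|---|---|---|
| 0.2 | 0.404 (0.124) | 0.412 (0.126) | 1.01 |
| 0.3 | 0.407 (0.124) | 0.427 (0.127) | 1.04 |
| 0.5 | 0.406 (0.124) | 0.463 (0.132) | 1.16 |
| 0.6 | 0.410 (0.124) | 0.497 (0.138) | 1.19 |

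The adjusted standard deviation is slightly larger. The gain comes from the estimate moving further from zero, as expected when a logit model conditions on a prognostic covariate.

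**No interaction.** If the OR were 2.0 at the first post-operative visit and 1.2 at 1 year, the model would report 1.53, or 1.31 with the preoperative visit included.

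**The case against.** The strongest reply is that nothing in 11.1 makes the preoperative visit a response. The model text does not mention it; only the shift-table item does. The presentation rule in SAP 8.6 concerns tables. Its sentence on trends also covers echocardiography and EQ-5D, and the models in 11.2.1 and 12.3 use baseline as a covariate. This reply stands as far as it goes: a reader might infer that the planned odds ratio is diluted, but the documents do not establish that. They leave the choice open, and the size of the result depends on it.

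A reader might also infer that the unadjusted odds ratio is biased or imprecise. It is neither. Randomization removes confounding, a marginal odds ratio is a valid target, and its standard error is slightly smaller than the adjusted one. Less efficient is the accurate description.

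On timing, the shift tables and by-visit summaries already give some information, and a common odds ratio is a legitimate summary. A treatment-by-visit term in a four-class model with unstructured correlation and probably sparse upper classes may not converge. Stratification factors are more debatable still, since the EQ-5D model does not list them either. Both are optional.

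**Conclusion.** The point holds as a gap in specification with a free improvement, and it is minor. If the preoperative visit is a response, the log odds ratio shrinks by about 35–39% with 1 pre + 2 post visits and 16–29% with 1 pre + 6 post. If it is not, the efficiency forgone is about 1–4% at baseline correlation 0.2–0.3 and 16–19% at 0.5–0.6. All of these sizes rest on assumed class distributions and correlations. With entry restricted to class II or higher, the baseline correlation could be weak and the loss negligible. No loss of power is stated, because the documents give no NYHA effect size or distribution from which to compute one.

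A reader might think that a trial conclusion is at risk. The documents do not support that. NYHA class is not separately listed among the secondary endpoints in Protocol 8.5.8. It enters the clinical efficacy composite in SAP 18.12, but that composite does not use this model. No hypothesis or success claim is attached to the odds ratio.

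**What to change.** In SAP 11.1, state that only post-operative NYHA assessments are responses, and add preoperative NYHA class as a covariate, in line with 11.2.1 and 12.3. As a supportive output, show the odds ratio at each post-operative visit through a treatment-by-visit term, if that model converges.

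The cost is SAP wording; no new data are needed. The one consequence to accept is that the odds ratio becomes conditional on baseline class and will usually lie further from 1 than the marginal one, so the report should label it as conditional.

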11.2. SITE REPORTED ECHOCARDIOGRAPHIC DATA

11.2.1. Hemodynamic data

Mean changes from baseline in site-reported valve hemodynamic

- mean gradient,
- peak gradient and
- LV mass

will be analyzed based on data observed while the subject remains on study (observed cases) as well as data imputed using multiple imputation (MI) methodology for time points at which no value is observed.

Multiple imputation will be performed under the assumption of missing-at-random (MAR) and will be implemented in two steps:

- First, partial imputation assuming MAR will be carried out to impute intermittent (non-monotone) missing data based on a multivariate joint Gaussian imputation model using the Markov chain Monte Carlo (MCMC) method. A separate imputation model will be used for each treatment arm. The imputation models will include countries, surgical approach, gender, age, hemodynamic assessments at each time point from Baseline. The MCMC method will be used with multiple chains, 200 burn-in iterations, and a non-informative prior. In case of non-convergence or non-estimability issues, a single model will be considered with treatment arm added as explanatory variable to the model.
- The remaining monotone missing data will be imputed using sequential regression multiple imputation, where a separate regression model is estimated for imputation of each variable

(i.e., measurement at each time point). Each regression model will include explanatory variables for country, surgical approach, gender, age, treatment and all previous values of hemodynamic assessment from baseline.

No rounding or range restrictions will be applied to imputed continuous values.

Imputed data will consist of 200 imputed datasets. The random seed number for partial imputation with the MCMC method will be 200582, and the random seed number for the sequential regression multiple imputation will be 4112.

Each of the 200 imputed datasets will be analyzed using observed and imputed data.

Change in hemodynamic assessment from baseline to 1-year (5-year) visit will be analyzed by means of a mixed regression model analysis including the treatment, hemodynamic assessment at baseline, country, surgical approach, gender, and age.

Treatment group comparison at Visit T will be based on the least squares mean (LSM) difference between treatment groups in change from baseline in hemodynamic assessment estimated by the analysis model in each of the imputed datasets. Results from analysis of each imputed dataset, i.e., LSM treatment differences and their standard errors, will be combined using Rubin's imputation rules to produce a pooled LSM estimate of treatment difference, its 95% confidence interval, and a pooled p-value for the test of null hypothesis of no treatment effect.

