8.3 PREOPERATIVE CT-SCAN

In current contemporary cardiac surgery practices, preoperative cardiac CT-scan is routinely done in the majority of cases to aid an appropriate surgical planning (including TAVI) for aortic valve replacement [2]. This standard diagnostic imaging modality allows optimal patient preparation and evaluation of anatomical characteristics such as the position of the aorta, measurement of the annulus, and presence of calcification [2]. Moreover CT-Scan will allow preoperative determination of the presence of aneurismal dilation, dissection of the ascending aortic wall, and presence of congenital bicuspid valve. All this information allows the surgeon to choose the appropriate valve size and surgical approach (i.e. appropriateness of minimally invasive approach). CT-scan will be performed in order to plan a possible mini-sternotomy in order to visualize the anatomical position of the aortic valve which will

influence the length of the mini-sternotomy (3rd or 4th intercostal space) and also the anatomical position of the aorta (midline or displaced to the right side). Detecting the presence of extensive calcification of the aorta can influence the site of aortic cross-clamping and whether a median sternotomy will be more appropriate.

For this randomized trial the included population will undergo a standard cardiac CT-scan prior to randomization. The minimum required measurement to be collected and reported are, but not limited to: aortic annulus diameter (short axis and long axis), LVOT diameter, STJ diameter, sinus of Valsalva diameter, ascending aorta diameter, aortic root height. In case of renal insufficiency a non-contrast injected CT-scan of the aorta can be performed. Standardized CT manufactured software for dimension measurement software tools can be used or generally available software like (i.e. 3-Mensio) is recommended

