8.5.7 RANDOMIZATION

Only subjects who have undergone standard chest CT-scan to determine if the aortic stenosis can be replaced with an available Perceval valve (size), and is potentially suitable for mini-sternotomy, may be randomized. For each subject the randomization will be performed based on the randomization list after enrollment and before valve operation, specifically after CT scan and surgical approach ("full sternotomy" or "mini-sternotomy") has been determined, to minimize bias.

Subjects will be randomly assigned in equal numbers (1:1) to one of two treatment arms. The blocked randomization list will be performed before the study start. The randomization will be stratified with 2 stratification factors, by country and by surgical approach (full sternotomy” or “mini-sternotomy”).

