8.5.9 SUB STUDIES

CT-scan

The collection of the data with the preoperative CT-scan for surgical planning will allow a direct comparison of the measurement done using this imaging system and the measurement done with dedicated valve sizers. Once the aorta of the subject is exposed, the aortic annulus is measured by a standard universal sizers (e.g. Hegar dilator) and the valve's specific sizers. These measurements will allow assessment of the concordance of the aortic annulus size determined by CT-scan with the valve size implanted; and allow a comparison of hemodynamic parameters based on the true annulus size independent of the prosthetic size.

Echocardiography sub-study (Participating Centers Only)

In addition to the echo parameters collected for all the subjects, one fourth (approximately 300 patients) of the trial population will have a complete echocardiographic examination that will be sent to a Core Lab for independent evaluation of the hemodynamic performance in the two treatment groups. At selected centers all patients will be recruited with the agreement to perform the echocardiographic assessment as required by the study guidelines.

The MedStar Health Research Institute, located at MedStar Washington Hospital Center, Washington D.C., USA will serve as the echo Core Laboratory for this clinical trial. [name] and [name] will serve as the Core Laboratory principal investigators.

For this subgroup of subjects the echocardiographic examination is planned at hospital discharge, at the 1-3 month visit, and at the 1, 3 and 5 years visits.

The Core lab may request for the submission of a test echo performed according to the TTE protocol to verify completeness and ensure compatibility, readability prior to enrolling the first subject.

Each postoperative TTE should include all the views and measurements specified on the Site Echo Case Report Form and the echocardiographic protocol (Appendix 5). A copy of the examination will be recorded and will be sent to the Echo Core Laboratory.

The Core Lab will conduct a full analysis of the acquisitions and perform the required analysis, following a completed Core Lab CRF, and send the results to the Sponsor. The Core Lab will discuss any discrepancies or data quality problems through the Sponsor with the clinical site as necessary.

Pacemaker evaluation

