8.4. CT SCAN

The characteristics of native valves measured preoperatively by CT scan are: LVOT diameter, Aortic Annulus mean diameter, Annulus perimeter, Annulus surface, Sinus of Valsalva diameter, Sino tubular junction (STJ) diameter, Ascending aorta, and Ratio STJ/annulus.

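### The haemodynamic comparison in SAP 11.2.1 leaves out CT annulus size, a required pre-randomisation measurement, and the SAP specifies no annulus-based comparison; the cost is precision, not validity.

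*SAP*

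**What the plan says.** **Analysis model.** SAP 11.2.1 analyses change from baseline in three site-reported outcomes (mean gradient, peak gradient, LV mass) with a "mixed regression model analysis including the treatment, hemodynamic assessment at baseline, country, surgical approach, gender, and age". The pooled result is one least-squares mean difference between arms.

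**Imputation models.** For intermittent gaps, "The imputation models will include countries, surgical approach, gender, age, hemodynamic assessments at each time point from Baseline". The second step, for monotone gaps, uses country, approach, gender, age, treatment and earlier haemodynamic values. Neither step contains an annulus measure.

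**Availability of CT annulus size.** Protocol 8.3: "For this randomized trial the included population will undergo a standard cardiac CT-scan prior to randomization". The minimum measurements there include "aortic annulus diameter (short axis and long axis), LVOT diameter, STJ diameter". Protocol 8.5.7 makes the CT a condition of randomisation. There is one exception in technique: "In case of renal insufficiency a non-contrast injected CT-scan of the aorta can be performed".

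**Stated use.** The CT-scan paragraph of Protocol 8.5.9 says the CT and sizer measurements will show how well CT annulus size agrees with the implanted size, and will "allow a comparison of hemodynamic parameters based on the true annulus size independent of the prosthetic size".

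**Use in the SAP.** SAP 8.4 opens its list with "The characteristics of native valves measured preoperatively by CT scan are" and includes annulus mean diameter, perimeter and surface, as baseline characteristics only. Annulus size is not among the subgroups (SAP 5.3) and no annulus-based analysis appears in the derivations (SAP 18.12). SAP 3.1 declares no changes from the protocol.

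**The concern.** The model uses the native-valve value as its baseline covariate but not the anatomical measurement that bears on which prosthesis fits. Protocol 5.3.1 assigns the four Perceval sizes by annulus bands running from 19-21 mm to 25-27 mm. Protocol 8.2 leaves the control valve to the investigator's choice among approved stented valves, so labelled size is not a common scale across arms. CT annulus diameter is such a scale, and it is fixed before randomisation.

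The native gradient is unlikely to stand in for it. The entry criteria select severe stenosis, with a mean gradient above 40 mmHg as one qualifying route, whereas Protocol 6.2 reports mean gradients of about 9 mmHg after Perceval implantation.

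Three things are at stake: a confidence interval wider than it needs to be, a haemodynamic difference more exposed to chance imbalance in annulus size, and a sub-study purpose for which no analysis is written down.

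**Working it through.** **1. Is there a plan figure to reproduce?** Not for this comparison: the documents state no SD, effect size or power for haemodynamics. The only design power is for the primary endpoint (0.805 at 91% event-free in both arms). It serves here only to check the number per arm. With 10% attrition, 1234 × 0.9 / 2 = 555. Then Φ(0.05 / √(2 × 0.91 × 0.09 / 555) − 2.005) = 0.818, close to 0.805, so 555 per arm is a reasonable working number.

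**2. Gain from adding annulus size.** Let r be the partial correlation of CT annulus size with the outcome, given the planned covariates. It is an assumption.
- Residual variance falls by r².
- The standard error and interval width fall by 1 − √(1 − r²).
- The equivalent increase in patients is 1/(1 − r²) − 1.
- The difference detectable at two-sided 0.05 with 80% power is (1.960 + 0.842) × √(2/555) × √(1 − r²), in residual SDs. Without annulus size it is 0.168.

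| r | Variance reduction | CI narrower by | Equivalent extra patients | Detectable difference (SD) |
|---|---|---|---|---|
| 0.1 | 1% | 0.5% | 1% | 0.167 |
| 0.2 | 4% | 2.0% | 4% | 0.165 |
| 0.3 | 9% | 4.6% | 10% | 0.160 |
| 0.4 | 16% | 8.3% | 19% | 0.154 |
| 0.5 | 25% | 13.4% | 33% | 0.146 |

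**3. Allowing for gender, already in the model.** Suppose gender explains a share g of annulus variance and acts on the outcome only through annulus size. With raw correlation ρ, the partial R² is 1 − (1 − ρ²)/(1 − gρ²). At an assumed g = 0.4, ρ of 0.2, 0.3, 0.4 and 0.5 gives partial R² of 0.02, 0.06, 0.10 and 0.17. The interval narrows by 1.2%, 2.8%, 5.3% and 8.7%.

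**4. Bias.** In 2,000 simulated trials of 1,110 patients with gender in the model and no true effect, the mean treatment estimate lay between 0.0002 and 0.0023 SD, with or without annulus size. The standard error fell by about 3% at ρ = 0.3 (0.0577 to 0.0560) and about 8% at ρ = 0.5 (0.0571 to 0.0526). The omission costs precision only.

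**5. Chance imbalance.** An annulus difference at its 95% chance limit is 1.96 × √(2/555) = 0.12 SD. It shifts the unadjusted estimate by 1.96 × r standard errors: 0.2 at r = 0.1 and 1.0 at r = 0.5. The baseline test in SAP 8 (p < 0.0005, z = 3.48) needs a difference of 3.48 × 0.0600 = 0.21 SD before it flags anything, so an imbalance of that size would normally pass unremarked.

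**6. Core-lab cohort.** Protocol 8.5.9 expects about 300 patients. With the same 10% attrition (assumed), 135 per arm gives a detectable difference of 2.802 × √(2/135) = 0.341 SD without annulus size, and 0.325 SD at r = 0.3. SAP 8.6 points to section 11.2 for trends, but that section is headed site-reported and models only site data. Core-lab values are therefore presented descriptively by arm.

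**The case against.** The strongest reply is that the planned model is valid and defensible as it stands. Allocation is randomised, the covariates are prespecified and include the stratification factors, and the confidence interval already reflects chance imbalance on average over repeated trials. CT measurements are tabulated and compared by arm. All of this stands. A reader might infer that the gradient comparison is biased without annulus size; the documents give no ground for that, and step 4 shows the opposite.

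A reader might also infer that the protocol promises an annulus-based analysis that will never be done. Protocol 8.5.9 says only that the measurements will allow one. Secondary endpoints 9 and 10 do not mention annulus size, and SAP 4.5 leaves room for later analyses by amendment or separate document. The comparison is unspecified in this SAP, which is a weaker statement. Nor does Protocol 8.5.9 say whether the true annulus size is the CT or the sizer value.

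A third tempting reading is a gain worth 10% to 33% more patients. That holds only for r between 0.3 and 0.5, a range the documents do not support over lower values, and gender probably takes up part of the correlation. The argument about native gradients also does not carry over to LV mass, where baseline LV mass is the covariate.

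Two limits apply to the remedy. Non-contrast CT in renal insufficiency may leave annulus values missing or less exact. And a main-effect covariate still yields a single treatment difference, so on its own it does not supply a comparison by annulus size.

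**Conclusion.** The point holds as a low-cost improvement to a secondary analysis. A required pre-randomisation covariate is missing from the SAP 11.2.1 analysis model and both imputation models, and the comparison mentioned in Protocol 8.5.9 has no specified analysis. The treatment estimate is unbiased either way and the primary endpoint is unaffected.

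The gain rests on an assumed partial correlation. Over 0.1 to 0.5 the interval narrows by about 0.5% to 13%, more plausibly in the lower part of that range, and possibly by a different amount for LV mass. It would be wrong to present this as a validity failure or a broken commitment.

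**What to change.** - Add CT aortic annulus mean diameter as a continuous covariate to the SAP 11.2.1 analysis model and to both imputation steps, so that the models stay compatible.
- State a rule for missing CT annulus values, for example including annulus diameter among the variables to be imputed.
- Use the CT value for adjustment, not sizer readings or labelled valve size, because those arise after randomisation. State which measurement Protocol 8.5.9 means by true annulus size.
- To deliver that comparison, prespecify gradients by CT annulus size and arm, with a treatment-by-annulus term labelled exploratory.
- Apply the same adjusted model to the core-lab cohort. First settle which baseline it uses: secondary endpoint 10 lists a preoperative core-lab reading, but the sub-study schedule in Protocol 8.5.9 starts at discharge.
- If the sponsor chooses not to do this, record the omission in SAP 3.1.

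The cost is SAP wording and some programming. No new data collection is needed.
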